11.1 Efficacy analysis

Complete and specific details of the final statistical analysis will be described and fully documented in the Statistical Analysis Plan (SAP). The SAP will be finalized prior to the database lock. The analysis will be performed using the statistical software package IBM SPSS. Demographic and baseline characteristics will be summarized. The number of observations, mean, standard deviation, median, minimum and maximum will be summarized for continuous variables. Discrete variables will be summarized by counts and percentages.

Primary analysis will be a per protocol approach, including all patients who completed the final visit (week 48). Missing data related to exploratory endpoints will be handled by last observation carried forward (LOCF) procedure.

The primary efficacy variables will be the number of patients that maintain CTx-I within the premenopausal reference range at week 48. Secondary efficacy variables will be the changes from baseline to week 12, 24 and 48 for CTx-I and P1NP levels. Co-exploratory variables will be DXA changes from baseline to week 24 and 48. Hand OA-related exploratory efficacy variables will be changes in NRS pain from baseline to week 12, 24 and 48, and changes in number of new erosive joints on X-rays and changes in GUSS values from baseline to W24 and 48.

All analyses be summarized by treatment group where treatment group equals 'exposed to Alendronate for 48 weeks Vs Alendronate for 24 weeks'.

11.2 Safety analysis

Safety analyses will be carried out using the safety population, which includes all subjects who received at least one dose of study drug. Treatment-emergent AEs and SAEs will be summarized and reported. The number and percentage of subjects experiencing adverse events will be provided by system organ class and Medical Dictionary for Drug Regulatory Activities (MedDRA) preferred term. In addition, summary of AEs by severity and relationship to study drug will be presented. Serious, severe AEs, or AEs that lead to premature study discontinuation will be listed and described in detail. Mean change in vital signs and laboratory variables at each visit will be summarized for all treated subjects, and compared between treatment groups using one way Analysis of Variance (ANOVA).

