Hypocalcemia must be corrected before initiating therapy with alendronate. Other disorders affecting mineral metabolism (such as vitamin D deficiency) should also be effectively treated. In patients with these conditions, serum calcium and symptoms of hypocalcemia should be monitored during therapy with alendronate. Presumably due to the effects of alendronate on increasing bone mineral, small, asymptomatic decreases in serum calcium and phosphate may occur. Patients should receive adequate calcium and vitamin D intake.

Osteonecrosis of the jaw (ONJ), which can occur spontaneously, is generally associated with tooth extraction and/or local infection with delayed healing, and has been reported in patients taking bisphosphonates, including alendronate sodium. Known risk factors for osteonecrosis of the jaw include invasive dental procedures (e.g., tooth extraction, dental implants, boney surgery), diagnosis of cancer, concomitant therapies (e.g., chemotherapy, corticosteroids, angiogenesis inhibitors), poor oral hygiene, and co-morbid disorders (e.g., periodontal and/or

August 09 2019 – Version 1.0

other pre-existing dental disease, anemia, coagulopathy, infection, ill-fitting dentures). The risk of ONJ may increase with duration of exposure to bisphosphonates. For patients requiring invasive dental procedures, discontinuation of bisphosphonate treatment may reduce the risk for ONJ. Clinical judgment of the treating physician and/or oral surgeon should guide the management plan of each patient based on individual benefit/risk assessment.

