	Alendronate Sodium*	Placebo	Alendronate Sodium**	Placebo		
	%	%	%	%		
	(N=196)	(N=397)	(N=3236)	(N=3223)		
Gastrointestinal						
Abdominal pain	6.6	4.8	1.5	1.5		
Nausea	3.6	4.0	1.1	1.5		
Dyspepsia	3.6	3.5	1.1	1.2		
Constipation	3.1	1.8	0.0	0.2		
Diarrhea	3.1	1.8	0.6	0.3		
Flatulence	2.6	0.5	0.2	0.3		
Acid regurgitation	2.0	4.3	1.1	0.9		
Esophageal ulcer	1.5	0.0	0.1	0.1		
Vomiting	1.0	1.5	0.2	0.3		
Dysphagia	1.0	0.0	0.1	0.1		
Abdominal distention	1.0	0.8	0.0	0.0		
Gastritis	0.5	1.3	0.6	0.7		
Musculoskeletal						
Musculoskeletal (bone, muscle or joint) pain	4.1	2.5	0.4	0.3		
Muscle cramp	0.0		0.2	0.1		
Nervous system/psychiatric						
Headache	2.6	1.5	0.2	0.2		
Dizziness	0.0	1.0	0.0	0.1		
Special senses						
Taste perversion	0.5	1.0	0.1	0.0		

Table 1 Osteoporosis Treatment Studies in Postmenopausal Women Adverse Reactions Considered Possibly, Probably, or Definitely Drug Related by the Investigators and Reported in Greater Than or Equal to 1% of Patients

* 10 mg/day for three years

** 5 mg/day for 2 years and 10 mg/day for either 1 or 2 additional years

who had a history of peptic ulcer disease and gastrectomy and who was taking concomitant aspirin developed an anastomotic ulcer with mild hemorrhage, which was considered drug related. Aspirin and alendronate sodium were discontinued and the patient recovered. In the Study 1 and Study 2 populations, 49-54% had a history of gastrointestinal disorders at baseline and 54-89% used nonsteroidal anti-inflammatory drugs or aspirin at some time during the studies .

Laboratory Test Findings: In double-blind, multicenter, controlled studies, asymptomatic, mild, and transient decreases in serum calcium and phosphate were observed in approximately 18% and 10%, respectively, of patients taking alendronate versus approximately 12% and 3% of those taking placebo. However, the incidences of decreases in serum calcium to less than 8.0 mg/dL (2.0 mM) and serum phosphate to less than or equal to 2.0 mg/dL (0.65 mM) were similar in both treatment groups.

Weekly Dosing The safety of alendronate sodium 70 mg once weekly for the treatment of postmenopausal osteoporosis was assessed in a one-year, double-blind, multicenter study comparing alendronate 70 mg once weekly and alendronate 10 mg daily. The overall safety and

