The investigator will monitor each subject for clinical and laboratory (serum Ca⁺⁺ levels) evidence of adverse events on a routine basis throughout the study. The investigator will assess and record any adverse event in detail on the adverse event CRF including the date and time of onset, description, seriousness, severity, time course, duration and outcome, relationship of the adverse event to study drug, an alternate etiology for events not considered "probably related" to study drug, final diagnosis/syndrome (if known) and any action(s) taken. Adverse events, whether in response to a query, observed by study-site personnel, or reported spontaneously by the subject, will be recorded.

All adverse events will be followed to a satisfactory conclusion.

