10.1. Definition

Adverse Event

An **adverse event** is defined as any untoward medical occurrence in a subject or clinical investigation subject administered a pharmaceutical product and which does not necessarily have a causal relationship with this treatment. An adverse event can therefore be any unfavorable and unintended sign (including an abnormal laboratory finding), symptom, or disease temporally associated with the use of a medicinal product, whether or not the event is considered causally related to the use of the product.

Such an event can result from use of the drug as stipulated in the protocol or labeling, as well as from accidental or intentional overdose, drug abuse, or drug withdrawal. Any worsening of a pre-existing condition or illness is considered an adverse event. Laboratory abnormalities and changes in vital signs are considered to be adverse events only if they result in permanent or temporary discontinuation of treatment with effervescent alendronate, necessitate therapeutic medical intervention and/or if the investigator considers them to be adverse events.

An elective surgery/procedure scheduled to occur during a study will not be considered an adverse event. However, if a pre-existing condition deteriorates unexpectedly during the trial (*e.g.*, surgery performed earlier than planned), then the deterioration of the condition for which the elective surgery/procedure is being done will be considered an adverse event.

Serious Adverse Event

If an adverse event meets any of the following criteria, it is to be considered as serious:

An event that results in the death of a subject.
An event that, in the opinion of the investigator, would
have resulted in immediate fatality if medical intervention
had not been taken. This does not include an event that

August 09 2019 - Version 1.0

would have been fatal if it had occurred in a more severe form.

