#### 4.3 Safety data

Analysis of the safety data set will be performed. This will include the occurrence on incidence and severity of adverse events and serious adverse events. These will be categorized according to the involved organ systems. The number of the events will be reported and compared between both treatment groups. Changes in routine clinical laboratory tests (calcium, vitamin D, creatinine, urine and GFR) will also be analyses

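### No count or listing of low calcium values is planned, so an asymptomatic, untreated low value reaches the report only if the investigator calls it an adverse event

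*Protocol*

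**What the plan says.** **Analysis.** Protocol 11.2 states: "Mean change in vital signs and laboratory variables at each visit will be summarized for all treated subjects", and compares the arms by one-way ANOVA. SAP 4.3 (Safety data) adds "Changes in routine clinical laboratory tests (calcium, vitamin D, creatinine, urine and GFR) will also be analyses" and gives no method. SAP 5 summarises continuous variables by mean and SD. Individual description in Protocol 11.2 is limited to adverse events that are serious, severe or lead to premature discontinuation.

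**Adverse-event route.** The opening of Protocol section 10 has the investigator watch each subject, clinically and through serum calcium, for "evidence of adverse events on a routine basis throughout the study". Protocol 10.1 then restricts what counts: "Laboratory abnormalities and changes in vital signs are considered to be adverse events only if they result in permanent or temporary discontinuation of treatment", or if they "necessitate therapeutic medical intervention and/or if the investigator considers them to be adverse events". No calcium threshold is given. Events that are recorded are tabulated by number and percentage of subjects (Protocol 11.2).

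**Calcium and the drug.** Protocol 1.3 says "small, asymptomatic decreases in serum calcium and phosphate may occur". Protocol 4.8 reports mild, transient, asymptomatic calcium decreases in about 18% of patients on alendronate and 12% on placebo, with falls below 8.0 mg/dL (2.0 mM) similar in the two groups. The post-marketing part of 4.8 and Protocol section 8 both mention symptomatic hypocalcaemia, generally with predisposing conditions.

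**Schedule.** Protocol 5.1 and the study table place calcium at baseline, week 24 and week 48, and not at week 12.

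**The concern.** A low calcium is an event in a single patient, judged against a limit. The planned summary is an average, and the planned test compares two averages. If the adverse-event route does not pick up a low value, nothing else in the plan has to show it. The report could then state that mean calcium did not change and did not differ between arms, and leave the reader unable to tell whether any patient was below the limit.

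The protocol treats calcium as the laboratory value to watch. Hypocalcaemia is an exclusion criterion, it is the stated reason for supplementation, and calcium is the only laboratory test named for adverse-event monitoring. The earlier trials described in Protocol 4.8 were reported as proportions of patients with a decrease or below a cut-off. This trial collects the data for such a proportion but does not plan to report it.

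**Working it through.** The documents state no safety figure to reproduce, and Protocol 11.3 says no formal sample size calculation was done. The check is therefore a reading of the reporting routes, followed by arithmetic that is illustrative.

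**Step 1. Which cases reach the report?**

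| Low calcium that… | Route | Shown? |
|---|---|---|
| interrupts or stops the drug | adverse event (10.1) | yes |
| needs treatment | adverse event (10.1) | yes |
| causes symptoms | untoward symptom, hence adverse event (10.1) | yes |
| is asymptomatic and untreated | adverse event only if the investigator considers it one | depends on discretion |

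The gap is the last row.

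**Step 2. What one value does to the mean.** Input: n = 20 per arm (Protocol 3.1). Assumption, not in the documents: an individual fall of 0.2 to 0.5 mmol/L.

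- Shift in arm mean = fall / n.
- 0.2 / 20 = 0.010 mmol/L; 0.5 / 20 = 0.025 mmol/L.
- Two patients falling by 0.3 to 0.4 mmol/L: 2 × 0.3 / 20 = 0.03 and 2 × 0.4 / 20 = 0.04 mmol/L.

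**Step 3. What the between-arm ANOVA would show.** Simulation of 40,000 trials with 20 per arm. Assumptions, not in the documents: normal changes with SD 0.08, 0.10 or 0.12 mmol/L, and affected patients shifted down by 0.3 or 0.4 mmol/L. Share of trials with p < 0.05:

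| Patients affected | Significant |
|---|---|
| 1 of 20, one arm | about 5% |
| 2 of 20, one arm | about 8 to 9% |
| 3 of 20, one arm | 12 to 19% |
| 2 of 20 in each arm | under 1.5% |

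The last row needs no simulation in principle. Through week 24 both arms take the same drug, so an effect common to both cancels in the comparison. Only at week 48, when one arm has been off drug since week 24, do the arms differ in treatment.

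**Step 4. What a count would show.**

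- One case: 1/20 = 5%.
- Two cases: 2/20 = 10%, exact 95% CI 1.2% to 31.7%.
- No cases: exact two-sided upper limit 1 − 0.025^(1/20) = 16.8% for one arm, and 1 − 0.025^(1/40) = 8.8% for both arms pooled.

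A count is therefore informative even when it is zero.

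**Step 5. How often calcium may fall.** Assuming the 18% rate in Protocol 4.8 carries over, 20 × 0.18 = 3.6 patients per arm and 40 × 0.18 = 7.2 overall would have a decrease. The chance of at least one in an arm is 1 − 0.82^20 = 98.1%. These are decreases, not values below a limit. The documents give no rate for the latter.

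**The case against.** A reader might infer that a low calcium needing no action is excluded from adverse events by definition. The text does not support that. The last limb of Protocol 10.1 makes it an adverse event whenever the investigator considers it one, and section 10 directs the investigator to look at calcium for this purpose. Once recorded, it is counted by preferred term. Protocol section 2 also bases the safety evaluation on adverse-event incidence, so the laboratory means are not its main support.

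A reader might also infer that clinically important hypocalcaemia could pass unseen. That would require that nobody treated the value or interrupted the drug, and that an investigator assigned to watch calcium did not record it. Patients with hypocalcaemia are excluded and all subjects receive calcium and vitamin D. Protocol 4.8 found falls below 2.0 mM similar to placebo.

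Other points on this side:

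- Protocol 11.1 lists minimum and maximum among its descriptive statistics, which might expose an extreme value. They stand under the efficacy heading, the SAP names only mean and SD, and a minimum does not say how many patients were low.
- The ANOVA is not meant to detect single cases, so its low power for that is unsurprising. This is fair. It also means that the ANOVA cannot stand in for a count.
- A fixed 2.0 mmol/L count would presume a particular assay. The documents do not say whether calcium is total, ionised or albumin-adjusted. This stands, and so the laboratory's own limit is the one to use.
- No passage cited here names a fall in GFR or vitamin D as a harm of alendronate, so the point does not extend to shift tables for those tests.

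What remains is the asymptomatic, untreated low value, reported at discretion and without a threshold.

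**Conclusion.** The point holds as a modest reporting gap. Neither document plans a count or listing of low calcium values, and the summary they do plan cannot reveal individual ones. The structural parts rest on the text alone: averaging hides single values, and at week 24 the arm comparison cannot show a shared effect. The simulated rates in the working rest on assumed SDs and falls, and on an assumed number of affected patients; they are illustrative only.

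The gap does not touch the primary endpoint. It does not mean that hypocalcaemia with symptoms, treatment or drug interruption would be lost. The change is worth making because it uses data already collected and replaces unguided discretion with a complete record.

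**What to change.** In Protocol 11.2 and SAP 4.3 (Safety data), keep the mean change and add:

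1. The number and percentage of patients with serum calcium below the laboratory's own lower limit at baseline, week 24 and week 48, by arm, with exact 95% confidence intervals. The denominator is patients with a calcium result at that visit.
2. The same count pooled over both arms at week 24, when both have had the same drug.
3. A listing of every such value, whether or not it was recorded as an adverse event.

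The limit serves only for reporting and sets no rule for clinical management. Cost: a few lines of text, one table and one listing, with slightly longer safety output. No new samples or visits are needed.

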3.1 Study design and schematic

This is a randomized study to investigate the effect of effervescent alendronate on BTM after denosumab discontinuation.

At the earliest three months but no later than four months after the last denosumab injection, 40 subjects will be randomized to effervescent alendronate administered for either 24 (n=20) or 48 weeks (n=20). The randomization code will be generated by a randomization manager. Randomization will be done in blocks of four.

Study schematic

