5.1 Study procedures

A screening visit will include explanation and signing of the informed consent form and overview of in- and exclusion criteria in order to participate. If appropriate, a pregnancy test will be performed.

The maximum window allowed between the screening visit and the baseline visit is of 3 weeks.

Upon selection, patients will be included in the study during **the baseline visit**, which will include completion of NRS pain, a hand radiograph, Dual energy X-ray absorptiometry (DXA) and the laboratory investigations required. These will comprise a calcium and vitamin D status, kidney function tests (serum ureum, serum creatinine, GFR), bone turnover markers (BTM), and, if appropriate, a pregnancy test. A maximum of 45 ml of blood will be collected each visit.

Patients will be randomized to alendronate for 24 weeks or 48 weeks: study products (Steovess, alendronate 70mg every week) will then be provided to the patient. Calcium/Vit D supplementation will be installed.

Schedule of assessments are provided in detail as Appendix 1. Safety assessment is clarified in the safety paragraph.

At week 12: safety assessment NRS pain, BTM

At week 24: safety assessment, NRS pain, serum calcium levels and BTM, hand radiographs and DXA

At week 48: safety assessment, NRS pain, hand radiographs, DXA and the laboratory investigations required. These will comprise a calcium and vitamin D status, kidney function tests (serum ureum, serum creatinine, GFR), and BTM.

Safety: Patients will be able to report any unwanted effect during the regular visits and through telephone contact at any time in between these visits. Templates for AE/SAE recording created by the sponsor will be used.

A negative pregnancy test will be an entry requirement in female premenopausal patients. Premenopausal patients at risk to become pregnant will be excluded if no valid anti-conceptive method is used. In practice, premenopausal women will be an absolute minority in this study population. All through the time of the study pregnancy tests will be done during the visits.

	Distribution IMP	Safety	Laboratory ¹				CR hand	DXA	NRS pain	
			Kidney function	BTM	Vit D	Ca++	Preg. test*		L	
SCREENING / BASELINE	х	х	x	х	х	х	х	Х	х	х
WEEK 12 (+/- 7 days)	х	х		x			х			х
WEEK 24 (+/- 7 days)	х	х	x	x		х	х	х	х	х
WEEK 48 (+/- 7 days)		Х	x	x	Х	х	х	Х	х	х
						appr	* if opriate			

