#### 5.3 Secondary outcome analysis

Bone density measures will be analysed in an intention to treat approach, using a linear mixed model. Data from all available time points will be used. Normal distribution will be checked and data transformations will be performed if necessary if assumptions of normality are not reached. P-values and estimated marginal means will be calculated at different time points.

In addition, percentage changes in BMD and the percentage of patients with a BMD loss higher than the least significant change (LSC), which represents the smallest difference between successive measurements of BMD that can be considered a real change, will calculated. Here no intention to treat approach will be used.

The number of patients exceeding reference ranges will be calculated with an intention to treat approach, where drop-outs will be considered as non-responders. A Fisher's exact test was used to assess differences in patient numbers exceeding reference ranges between both treatment groups.

All statistical tests were two-tailed and a p-value below 0.05 ( $\alpha$ ) was considered statistically significant.

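### Safety laboratory changes are compared by one-way ANOVA without baseline as a covariate: an unbiased comparison, but less precise than the collected data allow

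*Protocol*

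**What the plan says.** Protocol 11.2 defines the outcome as a change: "Mean change in vital signs and laboratory variables at each visit will be summarized for all treated subjects". Those changes are then "compared between treatment groups using one way Analysis of Variance (ANOVA)". No covariate is named. The population "includes all subjects who received at least one dose of study drug".

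The baseline laboratory values exist. Of the baseline investigations, Protocol 5.1 says: "These will comprise a calcium and vitamin D status, kidney function tests (serum ureum, serum creatinine, GFR), bone turnover markers (BTM)". The same section and the study table repeat calcium, vitamin D and kidney function at week 48.

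The protocol leaves the final method to the SAP: "Complete and specific details of the final statistical analysis will be described and fully documented in the Statistical Analysis Plan (SAP)". On these variables the SAP (4.3, Safety data) says only: "Changes in routine clinical laboratory tests (calcium, vitamin D, creatinine, urine and GFR) will also be analyses". It names neither a test nor a covariate. Its contents list shows no safety subsection under section 5, and its linear mixed models are assigned to turnover markers, bone density and hand pain. One-way ANOVA is therefore the only method named for safety laboratory values in the text available.

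**The concern.** A one-way ANOVA on change fixes the coefficient of baseline at 1. Unless baseline and follow-up are very highly correlated, that over-corrects: a patient with a high baseline tends to show a fall, and the scatter this produces stays in the error term. ANCOVA estimates the coefficient and removes the scatter.

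At stake is the width of the confidence intervals for the calcium, vitamin D and kidney-function differences. The sample cannot grow, since Protocol 11.3 limits it to patients leaving the parent study's extension, so the analysis is one of the few places where precision can still be gained. Calcium is also a variable the protocol treats as a safety matter: hypocalcaemia is an exclusion criterion (3.5.2), and serum calcium is monitored for adverse events (section 10).

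**Working it through.** **Figure to reproduce.** There is none. The plan gives no SD, effect size, correlation or precision target for these variables, and Protocol 11.3 reports no formal sample size calculation.

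**Inputs**
- n = 20 per arm. Protocol 3.1: "40 subjects will be randomized to effervescent alendronate administered for either 24 (n=20) or 48 weeks (n=20)".
- Outcome and test: change, one-way ANOVA (Protocol 11.2).
- Baseline and week-48 values: Protocol 5.1 and the study table.
- Assumed: correlation r between baseline and follow-up, taken from 0.3 to 0.95; equal SD at both times, set to 1; one linear slope common to both arms.

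**Step 1. Variance of the arm difference, ANOVA on change:** (2/n) × 2(1 − r).

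**Step 2. Variance of the arm difference, ANCOVA:** (2/n) × (1 − r²) × [1 + 1/(2n − 4)]. The last factor is the average cost of estimating the slope when baselines differ by chance. At n = 20 it is 1 + 1/36 = 1.028.

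**Step 3. Ratio of step 2 to step 1:** (1 + r)/2 × 1.028. The ratio of 95% CI widths is the square root of this, times 2.0262/2.0244 (t values on 37 and 38 degrees of freedom). The last column is 20 divided by the variance ratio.

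| r (assumed) | (1 + r)/2 | Variance ratio at n = 20 | CI width ratio | Per-arm n needed by ANOVA on change for the same variance |
|---|---|---|---|---|
| 0.3 | 0.650 | 0.668 | 0.818 | 29.9 |
| 0.5 | 0.750 | 0.771 | 0.879 | 25.9 |
| 0.7 | 0.850 | 0.874 | 0.936 | 22.9 |
| 0.9 | 0.950 | 0.976 | 0.989 | 20.5 |
| 0.95 | 0.975 | 1.002 | 1.002 | 20.0 |

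**Step 4. Break-even.** Equal CI widths need (1 + r)/2 × 1.0278 × (2.0262/2.0244)² = 1. The squared t ratio is 1.0018, so r = 2/(1.0278 × 1.0018) − 1 = 0.942.

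**Step 5. Checks.** Simulation of 15,000 trials at each of r = 0.3, 0.5, 0.7 and 0.9 gave squared standard-error ratios of 0.67, 0.77, 0.87 and 0.98. With only 16 per arm contributing, the formula gives 0.673, 0.777, 0.880 and 0.984, so moderate dropout does not alter the picture.

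**Step 6. Where chance imbalance enters.** The step 1 variance splits exactly: 2(1 − r) = (1 − r²) + (1 − r)². The second term is the part due to chance baseline differences. At r = 0.5 the split is 1.00 = 0.75 + 0.25. The imbalance effect is therefore already inside the variance ratio and must not be counted again.

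**The case against.** The case against acting is substantial.

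**Baseline is not ignored.** A reader might infer that the measured baseline goes unused. It does not: the outcome is change, so baseline is subtracted. Only its use as a covariate is missing.

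**There is no bias.** A reader might also infer that chance imbalance at 20 per arm biases the comparison. The arms are randomised, so the change-score difference is unbiased. In one realised trial a baseline difference of d SD does move the expected contrast by (1 − r)d in the opposite direction, but across randomisations that is variance, and step 6 shows it is already counted.

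**The sentence is in the protocol, not the SAP.** The SAP departs from the protocol elsewhere (R instead of SPSS, intention to treat instead of per protocol), so its silence does not prove that ANOVA will be used. This stands in part. The SAP does not withdraw ANOVA either, and a method left unnamed also needs a sentence.

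**The size is assumed.** This stands. Nothing in the documents shows where r lies for creatinine or GFR, and at 0.9 the gain is about 2%. The large-sample ratio (1 + r)/2 also slightly flatters ANCOVA at this sample size.

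**Little depends on it.** This stands too. The SAP's significance threshold is stated in the efficacy sections (in 5.3: "All statistical tests were two-tailed and a p-value below 0.05"), the safety comparison has no hypothesis or power target, and Protocol 10.1 lets individual laboratory abnormalities be recorded as adverse events.

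**Pooling the arms at week 24 does not follow.** Both arms are assigned alendronate to week 24, so pooling there may look like a natural companion change. It does not follow from a missing covariate. Protocol 11.2 already summarises changes for all treated subjects, and vitamin D is not scheduled at week 24.

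**Conclusion.** The point holds as one of precision, not validity. The only method named for safety laboratory changes omits baseline as a covariate, and the available SAP text puts nothing in its place. At 20 per arm, ANCOVA would cut the variance of the arm difference by about 33%, 23%, 13% and 2% at r of 0.3, 0.5, 0.7 and 0.9, with no gain above about 0.94. In patient terms, ANOVA on change would need about 50%, 30%, 14% and 2% more patients to match it. These figures rest on an assumed r, equal SDs at both times and a common linear slope.

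The documents do not support a claim that the planned comparison is biased or that the loss is large for every variable. The point is limited to laboratory values: Protocol 11.2 also mentions vital signs, but the study table schedules none, so a baseline for them cannot be confirmed. Importance is low.

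**What to change.** Add one sentence to SAP 4.3 (Safety data): week-48 calcium, vitamin D and kidney-function values will be compared between arms by ANCOVA with arm and baseline value as terms, and reported as an adjusted difference with a 95% confidence interval; this replaces the one-way ANOVA of Protocol 11.2 for laboratory values.

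The SAP is the natural place, because Protocol 11.1 assigns the final details to it. Changing Protocol 11.2 itself would also bring in the amendment steps of sections 16 and 17. The statistical cost is one degree of freedom (38 to 37) and, if r is very high, a negligible loss: a CI about 0.2% wider at r = 0.95. No new data are needed. If the laboratory comparison has already been run, the adjusted estimate can be added and labelled post hoc.
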